9.2 SETTING

This retrospective database study will leverage the GE EMR data from October 1, 2013 to April 30, 2018. The EMR consists of patient data from ambulatory care records in the US and is representative of the US population receiving healthcare in the ambulatory setting. Patients will be included in one of three study cohorts based on prescription history from October 1, 2014 to April 30, 2018, allowing for a 12-month pre-index period to describe patient demographic, clinical and treatment characteristics.

Index date

The index date for the nintedanib (or pirfenidone) cohort will be the date of the first nintedanib (or pirfenidone) prescription during the selection window (from October 1, 2014 to April 30, 2018). The index date for the untreated cohort will be the date of the earliest IPF diagnosis or a randomly assigned date between October 1, 2013 and April 30, 2018.

Pre-index period

[figure not shown]
The pre-index period for each cohort will be the 12 months prior to the index date. Patients will be required to have ≥ 1 diagnosis of IPF during the pre-index period (see additional inclusion criteria described below).

Post-index period

The post-index period for each cohort will start from the index date. Since the study aims to evaluate patient characteristics during the pre-index period, no minimum follow-up will be required for post-index period and no study measures will be assess during the post-index period.

Patient selection is illustrated in Figure 1.

Figure 1. Patient Selection

Nintedanib cohort

Inclusion criteria:

- With ≥ 1 diagnosis for IPF (the International Classification of Diseases, Ninth Revision, Clinical Modification [ICD-9-CM] codes 516.3, 516.31, 515,¹¹ or ICD-10-CM codes J84.112) in the EMR between October 1, 2013 to April 30, 2018
- With ≥ 1 prescription for nintedanib between October 1, 2014 and April 30, 2018 (the selection window)
 - The date of the first prescription will be defined as the index date
- With ≥ 1 record in the EMR database during the 12 months prior to the index date (the pre-index period)
- With ≥ 1 diagnosis of IPF during the 12 months prior to the index date
- Age ≥ 40 on the index date
- will explore also requiring ≥ 1 chest CT scan before first IPF diagnosis during the pre-index period¹²

Exclusion criteria:

- With ≥ 1 diagnosis of other known causes of interstitial lung disease (ILD) on the date of or after the first IPF diagnosis during the pre-index period^{12,13}

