- Other known causes of ILD include conditions such as systemic sclerosis, rheumatoid arthritis, systemic lupus erythematosus, dermatomyositis, polymyositis, Sjögren disease, and hypersensitivity pneumonitis (ICD-9-CM codes 135, 237.7, 272.7, 277.3, 277.8, 446.21, 446.4, 495, 500–505, 506.4, 508.1, 508.8, 516.0, 516.1, 516.32–516.37, 516.2, 516.8, 516.9, 517.0, 517.2, 517.8, 518.3, 555, 710.0, 710.0–710.4, 714.0, 714.81, 720, and 759.5, or ICD-10-CM equivalent codes)^{12,13}
- With ≥ 1 prescription for nintedanib prior to the index date
- With ≥ 1 prescription for pirfenidone prior to or on the index date

Pirfenidone cohort

Inclusion criteria:

- With ≥ 1 diagnosis for IPF (ICD-9-CM codes 516.3, 516.31, 515,¹¹ or ICD-10-CM codes J84.112) in the EMR between October 1, 2013 to April 30, 2018
- With ≥ 1 prescription for pirfenidone between October 1, 2014 and April 30, 2018 (the selection window)
 - The date of the first prescription will be defined as the index date
- With ≥ 1 record in the EMR database during the 12 months prior to the index date
- With ≥ 1 diagnosis of IPF during the 12 months prior to the index date
- Age ≥ 40 on the index date
- will explore also requiring ≥ 1 chest CT scan before first IPF diagnosis during the pre-index period¹²

Exclusion criteria:

- With ≥ 1 diagnosis of other known causes of interstitial lung disease (ILD) on the date of or after the first IPF diagnosis during the pre-index period^{12,13}
 - Other known causes of ILD include conditions such as systemic sclerosis, rheumatoid arthritis, systemic lupus erythematosus, dermatomyositis, polymyositis, Sjögren disease, and hypersensitivity pneumonitis (ICD-9-CM codes 135, 237.7, 272.7, 277.3, 277.8, 446.21, 446.4, 495, 500–505, 506.4, 508.1, 508.8, 516.0, 516.1, 516.32–516.37, 516.2, 516.8, 516.9, 517.0, 517.2, 517.8, 518.3, 555, 710.0, 710.0–710.4, 714.0, 714.81, 720, and 759.5, or ICD-10-CM equivalent codes)^{12,13}
- ≥ 1 prescription for pirfenidone prior to the index date
- ≥ 1 prescription for nintedanib prior to or on the index date

Untreated cohort

Inclusion criteria:

- With ≥ 1 diagnosis for IPF (ICD-9-CM codes 516.3, 516.31, 515,¹¹ or ICD-10-CM codes J84.112) in the EMR between October 1, 2013 to April 30, 2018
 - Index date will be defined as the date of the earliest IPF diagnosis or a randomly assigned date based on the exploratory analyses to be performed on the two treatment cohorts (exploring time from IPF diagnosis to treatment initiation)

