 - will explore requiring ≥ 2 diagnoses for IPF that are ≥ 30 days apart to improve the identification of IPF patients^{12,13}
- With ≥ 1 record in the EMR database during the 12 months prior to the index date (the pre-index period)

- Age ≥ 40 on the index date
- will explore also requiring ≥ 1 chest CT scan before first IPF diagnosis during the pre-index period¹²

Exclusion criteria:

- With ≥ 1 diagnosis of other known causes of interstitial lung disease (ILD) on the date of or after the first IPF diagnosis during the pre-index period
 - Other known causes of ILD include conditions such as systemic sclerosis, rheumatoid arthritis, systemic lupus erythematosus, dermatomyositis, polymyositis, Sjögren disease, and hypersensitivity pneumonitis (ICD-9-CM codes 135, 237.7, 272.7, 277.3, 277.8, 446.21, 446.4, 495, 500–505, 506.4, 508.1, 508.8, 516.0, 516.1, 516.32–516.37, 516.2, 516.8, 516.9, 517.0, 517.2, 517.8, 518.3, 555, 710.0, 710.0–710.4, 714.0, 714.81, 720, and 759.5, or ICD-10-CM equivalent codes)^{12,13}
- With prescription for nintedanib or pirfenidone anytime during the data window

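### Section 9.2 contradicts itself on whether untreated patients need an IPF diagnosis before index, and one stated index-date rule lets the index date precede that diagnosis

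*Combined protocol and SAP*

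**What the plan says.** All the relevant text is in Section 9.2 (Setting) of the combined protocol and SAP.

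- **General rule.** Under Pre-index period: "The pre-index period for each cohort will be the 12 months prior to the index date". The next sentence is "Patients will be required to have ≥ 1 diagnosis of IPF during the pre-index period (see additional inclusion criteria described below". No cohort is exempted.
- **Treated lists.** The nintedanib and pirfenidone inclusion criteria both carry the line "With ≥ 1 diagnosis of IPF during the 12 months prior to the index date".
- **Untreated list.** That line is absent. The diagnosis criterion is an IPF code "in the EMR between October 1, 2013 to April 30, 2018", not tied to index. The only firm inclusion criterion on the look-back concerns records of any kind: "With ≥ 1 record in the EMR database during the 12 months prior to the index date (the pre-index period".
- **Untreated exclusion.** Other known causes of ILD are counted from the first IPF diagnosis within the pre-index period, so the list presupposes a diagnosis that it does not require.
- **Untreated index date, first statement.** Under Index date: the earliest IPF diagnosis or "a randomly assigned date between October 1, 2013 and April 30, 2018".
- **Untreated index date, second statement.** In the untreated list: "Index date will be defined as the date of the earliest IPF diagnosis or a randomly assigned date based on the exploratory analyses" in the treated cohorts, where the time from diagnosis to treatment start is to be explored.

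**The concern.** A programmer working from the untreated list keeps patients whom the general rule drops. With a calendar-date draw, nothing in that list stops the index date from falling before the first IPF code. Such a patient's baseline year describes someone not yet recorded as having IPF, while every treated patient has IPF recorded in the year before index.

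Lung function tests, HRCT, oxygen therapy and steroid use are all baseline measures in Section 9.3.3, and all can be expected to change around diagnosis. Section 9.1 calls an ASD of at least 10% meaningful and uses the propensity model to find what drives initiation. A difference created by index timing could therefore be reported as a driver of treatment.

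**Working it through.** **1. The texts side by side.** Take an untreated patient with records before the drawn index date and a first IPF code after it. The general rule excludes the patient and the untreated list includes the patient. The ILD exclusion then cannot operate, because there is no IPF diagnosis in the pre-index period to count from. The exploratory rule of two IPF codes at least 30 days apart does not help, since both codes may follow index.

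**2. Share indexed before the first IPF code, by reading.**

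| Reading | Share |
|---|---|
| General pre-index rule enforced | 0% |
| Index = earliest IPF diagnosis | 0% |
| Random date = diagnosis + non-negative delay | 0% |
| Calendar date + untreated list as written | steps 3 and 4 |

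**3. Calendar draw, before the record criterion.** The plan gives no figure to reproduce. From the documents: October 1, 2013 to April 30, 2018 is 1,673 days (T = 4.58 years), and the selection window starts 365 days in. Assumed: index date uniform, and first IPF code uniform except for a fraction q of patients first coded in the first 6 months (182 days, mean 91).

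- Index over the full window: share = (1 − q)/2 + q × 91/1,673. For q = 0, 0.2, 0.4, 0.6 this gives 50%, 41%, 32%, 23%.
- Index from October 1, 2014 only: share = (1 − q) × (1,673 − 365)/(2 × 1,673) = (1 − q) × 0.391. This gives 39%, 31%, 23%, 16%.

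**4. Adding the record criterion, simplified to any record before index.** Assume that the time from first EMR record to first IPF code is exponential with mean m years. For the full window with q = 0, let A = m/T − (m/T)²(1 − e^(−T/m)); the share is A/(0.5 + A). For m = 1, m/T = 0.218, A = 0.171, and the share is 0.171/0.671 = 0.255. For m = 0.5, 2 and 5 the shares are 0.163, 0.347 and 0.430.

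Simulation with 1,000,000 draws agrees. With q = 0.4 it gives 10%, 15%, 21% and 27% for m = 0.5, 1, 2 and 5. The lowest scenario (q = 0.6, m = 0.5, index from October 1, 2014) gives 4%.

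**5. Look-back.** Data start on October 1, 2013, so any index date before October 1, 2014 lacks a full 12 months. That is 365/1,673 = 22% of the calendar range.

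**6. What a given share could do.** Illustration with assumed rates: oxygen use is 30% in treated patients and in diagnosed untreated patients, and 10% before diagnosis. With a share s indexed before diagnosis, the untreated rate is 0.30 − 0.20s. By the Section 9.7.1 formula for proportions:

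- s = 0.50: 0.10/√[(0.21 + 0.16)/2] = 0.23
- s = 0.30: 0.06/√[(0.21 + 0.1824)/2] = 0.14
- s = 0.22: 0.044/√[(0.21 + 0.1905)/2] = 0.10
- s = 0.04: 0.008/√[(0.21 + 0.2067)/2] = 0.02

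At these rates, a share of about 22% reaches the 10% threshold with no true difference among diagnosed patients; the lowest scenario comes nowhere near it.

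**The case against.** The strongest reply is that the passages can be read as one rule. The general requirement follows directly on a definition covering each cohort and calls the lists additional criteria, so silence in one list need not repeal it. The untreated ILD exclusion presupposes a pre-index diagnosis. The calendar range may only be a bound, with the treated diagnosis-to-initiation times as the method. Section 9.3.3 lists index years 2014 to 2018 for all cohorts, with no 2013. On that reading no one is indexed before diagnosis. Figure 1, which I could not see, may also bear on this.

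This shows that a consistent reading exists, but the text does not compel it. Both treated lists restate the requirement despite the general rule, so its absence from the third looks deliberate, and the calendar range is written as a rule for the date, not as a bound on another rule.

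Two further objections stand in full:

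- **Size.** A reader might infer that 30% to 50% of untreated patients would be indexed too early, or that enforcing the general rule would cut the cohort from 10,000 to about 2,000. The documents support neither. They give no distribution of diagnosis dates, the first range ignores the record criterion, and the second figure needs a calendar draw with IPF coded only once. The 10,000 is itself an early feasibility count.
- **Remedy.** Copying the treated line unchanged would exclude every untreated patient indexed at the earliest diagnosis, because no diagnosis can precede that date.

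**Conclusion.** The contradiction is real and should be reconciled before the cohort is programmed, because it decides who enters a comparison cohort. The risk is conditional: it needs both the calendar-date rule and the untreated list as written. In that case the share indexed before diagnosis lies between a few percent and about 50% in the scenarios tried. The 50% is approached only when few patients are coded early and record histories are long; with the record criterion modelled, the highest value was 43%. The range rests on assumed diagnosis timing and record history, and it is not a mathematical limit.

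The exposed analyses are nintedanib versus untreated, pirfenidone versus untreated, and the treated-versus-untreated propensity score. Nintedanib versus pirfenidone is unaffected. The 0% for the earliest-diagnosis option means only that index does not precede the first code. Its look-back still lies before diagnosis, which is a separate question about the choice of option.

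**What to change.** 1. Add to the untreated inclusion list at least one IPF diagnosis in the 12 months up to and including the index date, and align the general pre-index sentence with it. Counting the index day keeps the earliest-diagnosis option feasible and matches the Section 9.3.3 baseline window, which includes the index date unless otherwise noted.
2. Delete the calendar-range random date. If a random index is used, set it to the first IPF diagnosis plus a non-negative delay drawn from the treated diagnosis-to-initiation distribution. Restrict untreated index dates to the October 1, 2014 to April 30, 2018 selection window, so that each has a full look-back.
3. Re-estimate the untreated number under these criteria and report the losses in the attrition table.

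The cost is protocol wording and a few programming conditions. The untreated number may fall below the preliminary 10,000. Losses would include patients coded once whose drawn delay exceeds 12 months, and those whose index date falls outside the selection window.

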9.3.2.2 Secondary outcomes

The secondary outcomes will be the probabilities (propensity scores) of receiving one treatment over another (or probability of receiving antifibrotic treatment) between the following cohorts:

- Nintedanib vs. pirfenidone
- Treated patients (i.e., nintedanib or pirfenidone) vs. untreated

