9.3.3 Covariates

The following measures will be evaluated during the 12-month baseline period, including index date, unless otherwise noted. Measures will be reported separately for each of the three cohorts.

For nintedanib and pirfenidone cohorts only:

- Index medication (n, %)
 - Nintedanib
 - Pirfenidone
- Average daily dose of the index prescription
 - Nintedanib (mean, SD, median, min, max) and categories (n, %)
 - 100 mg
 - 150 mg
 - Unknown
 - Pirfenidone (mean, SD, median, min, max) and categories (n, %)
 - 267 mg
 - Unknown
- Time from the earliest diagnosis for IPF to index (mean, SD, median, min, max)
- Prescribing physician specialty (n, %)
 - Primary care
 - Internal medicine
 - Pulmonologist
 - Other

For all cohorts:

Demographic characteristics

- Age (mean, SD, median, min, max) and age categories on index date (n, %)
 - 40-49
 - 50-59

- 60-69
 - ≥ 70
- Gender (n, %)
 - Male
 - Female
- Index year (n, %)
 - 2014
 - 2015
 - 2016
 - 2017
 - 2018
- Region (n, %)
 - Northeast
 - Midwest
 - South
 - West
- Race/ethnicity (n, %) (expected to be missing for about 40% of patients)
 - White
 - African American
 - Hispanic
 - Asian
 - Other
 - Unknown
- Payer type (n, %)
 - Commercial
 - Medicaid
 - Medicare
 - Self-Insured
 - Other/Unknown

Clinical characteristics (based on ICD-9/10-CM procedure and diagnosis codes, laboratory test codes, CPT codes and NDC/RxNorm (to be included in Appendix), as well as other information in the EMR encounter files)

- Body weight (lbs; mean, SD, median, min, max)
 - Body mass index (BMI; kg/m²; mean, SD, median, min, max)
 - BMI category, defined using BMI field (n, %)
 - Underweight ($<18.5 \text{ kg/m}^2$)
 - Normal weight (18.5 to 24.99 kg/m²)
 - Overweight (25 to 29.99 kg/m²)
 - Obese (30 to 34.99 kg/m²)
 - Very obese ($\geq 35 \text{ kg/m}^2$)

- Blood pressure (BP)¹⁴ (n, %)
 - Diastolic BP
 - Normal (<80 mmHg)
 - High (≥ 80 mmHg)
 - Systolic BP
 - Normal (<120 mmHg)
 - Elevated (≥ 120 and < 129 mmHg)
 - High (≥ 130 mmHg), further broken down as follows if data allow
 - Stage 1 (≥ 130 and < 139 mmHg)
 - Stage 2 (≥ 140 mmHg)
- Smoking status at index (n, %); excluding smokeless tobacco; categories to be finalized during analysis
 - Smoker
 - Non-smoker, further broken down as follows if data allow
 - Previous smoker
 - Never smoker
 - Unknown/missing
- Alcohol consumption (n, %)
 - Yes
 - No
 - Unknown/missing

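### Section 9.2 waives observation after diagnosis for every cohort, but untreated status depends on it, so some late-diagnosed future initiators are counted as untreated

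*Combined protocol and SAP*

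**What the plan says.** Section 9.2 (Post-index period) states for each cohort that "no minimum follow-up will be required for post-index period and no study measures will be assess during the post-index period". The reason given is that the study evaluates pre-index characteristics.

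The same section excludes from the untreated cohort any patient "With prescription for nintedanib or pirfenidone anytime during the data window". The study "will leverage the GE EMR data from October 1, 2013 to April 30, 2018", and patients enter cohorts "based on prescription history from October 1, 2014 to April 30, 2018".

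The untreated index date is left open. It is "the date of the earliest IPF diagnosis or a randomly assigned date between October 1, 2013 and April 30, 2018", or, in the untreated inclusion criteria, the earliest diagnosis or "a randomly assigned date based on the exploratory analyses to be performed on the two treatment cohorts". Requiring two IPF diagnoses at least 30 days apart is only to be explored.

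Section 9.3.3 plans to describe the time from earliest IPF diagnosis to index in the two drug cohorts, so the plan expects a lag. The untreated cohort enters two of the three primary comparisons (Section 9.3.2.1) and one of the two propensity models, "Treated patients (i.e., nintedanib or pirfenidone) vs. untreated" (Section 9.3.2.2).

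**The concern.** A drug-cohort patient's status is fixed by the prescription on the index date, and nothing later changes it. An untreated patient's status is fixed by what is seen, or not seen, between diagnosis and the end of data. The waiver in Section 9.2 treats the two situations alike.

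A patient first coded with IPF on April 20, 2018 has 10 days in which a prescription could be recorded. One first coded in early 2015 has more than three years. Both carry the same label. If the first patient starts an antifibrotic in June 2018, a future initiator sits in the comparator.

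At stake are the nintedanib-versus-untreated and pirfenidone-versus-untreated standardized differences and the treated-versus-untreated propensity model. To the extent that future initiators resemble current initiators, they pull these contrasts toward zero. The bias section (9.12) deals with switching and with misclassification of IPF. The limitations section (9.9) deals with prescribed patients who never took the drug. Neither addresses this error.

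**Working it through.** The plan states no figure on this point, so there is none to reproduce. What follows is an illustration under stated assumptions.

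**Inputs from the documents.** Data window October 1, 2013 to April 30, 2018, 55 months; selection window from October 1, 2014, 43 months (Section 9.2). Observed starters 868 + 615 + 144 = 1,627, matching Table 1, and about 10,000 untreated (Section 9.5). Meaningful difference: 10% (Section 9.7.1).

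**Assumptions.** Diagnoses uniform over T = 55 or 43 months. Exponential time from diagnosis to first prescription among eventual starters, with median m = 3, 6 or 12 months and λ = ln 2/m. Death and departure from the EMR network are ignored.

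**Step 1: future starters counted as untreated.** Share of eventual starters not yet seen to start: u = (1 − e^(−λT))/(λT). Eventual starters: E = 1,627/(1 − u). Misclassified: M = E − 1,627. For T = 55 and m = 12: λT = 3.177, u = 0.302, E = 2,330, M = 703.

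**Step 2: concentration in late diagnoses.** Misclassified among those diagnosed in the last 6 months: L = (E/T)(1 − e^(−6λ))/λ. All untreated diagnosed then: (10,000 − M)·6/T + L. For T = 55 and m = 12: L = 215, and 215/(1,014 + 215) = 17.5%.

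**Step 3: dilution.** If misclassified patients resemble the treated, a true standardized difference of 0.100 becomes about 0.100 × (1 − M/10,000).

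| T | m | u | M | % of 10,000 | % of untreated diagnosed in last 6 months | 0.100 becomes |
|---|---|---|---|---|---|---|
| 55 | 3 | 0.079 | 139 | 1.4 | 8.8 | 0.099 |
| 55 | 6 | 0.157 | 303 | 3.0 | 12.6 | 0.097 |
| 55 | 12 | 0.302 | 703 | 7.0 | 17.5 | 0.093 |
| 43 | 3 | 0.101 | 182 | 1.8 | 9.1 | 0.098 |
| 43 | 6 | 0.200 | 407 | 4.1 | 13.3 | 0.096 |
| 43 | 12 | 0.369 | 952 | 9.5 | 19.4 | 0.090 |

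**Step 4: calendar time.** With T = 43 and untreated patients indexed at diagnosis, starters indexed between months a and z number (E/T)[G(z) − G(a)], where G(t) = t − (1 − e^(−λt))/λ. Of those diagnosed between a and z, (E/T)[e^(−λ(T−z)) − e^(−λ(T−a))]/λ are not yet treated at data end.

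| m | Treated share by diagnosis year, 2014 and 2018 | Treated share by index year, 2014, 2016, 2017, 2018 |
|---|---|---|
| 3 | 16%, 5% | 5%, 15%, 15%, 14% |
| 6 | 17%, 3% | 3%, 16%, 16%, 15% |
| 12 | 20%, 2% | 2%, 16%, 17%, 17% |

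**Step 5: effect of a cut-off at X = 12 months.** For T = 55 and m = 12, patients diagnosed in the last 12 months are removed. Future starters removed: (E/T)(1 − e^(−12λ))/λ = 367. Other untreated removed: 9,297 × 12/55 = 2,028. That leaves 10,000 − 2,395 = 7,605 untreated, of whom 703 − 367 = 336 (4.4%) are still future starters, against 7.0% before. Treated removed: 2,330 × 12/55 − 367 = 141, or 8.7% of 1,627. Over all six scenarios, the untreated loss is 23% to 30%, the treated loss 9% to 21%, and the remaining contamination 0.1% to 6.2%.

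**Step 6: precision.** Section 9.7.1 gives σ[d] = √((n₁+n₂)/(n₁n₂) + d²/(2(n₁+n₂))). At d = 0.1 against 10,000 untreated this is 0.042 for 615 nintedanib patients and 0.035 for 868 pirfenidone patients. In the worst scenario (T = 43, m = 3), 20.5% of treated patients are lost and 7,089 untreated remain. The values become 0.047 (n₁ = 489) and 0.040 (n₁ = 690), if both drugs lose the same share.

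**The case against.** The strongest reply is that the study is descriptive. The abstract defines the controls by an observed status within the selection window, not as never treated. On that view nobody is misclassified, and a limitation statement would do. This has some force, and it argues for proportion. But the plan does not use status at index: it removes early-diagnosed patients who start later and cannot see late-diagnosed patients who will. The label therefore means different things by diagnosis date, in a study meant to find what drives initiation.

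A second reply is that the open options already help. If the treated cohorts' lag is added to the diagnosis date, and patients whose drawn date falls after April 30, 2018 are dropped, some late diagnoses go. Requiring two diagnoses at least 30 days apart would remove the April 20 patient. This is fair, but neither option is fixed. The first needs a dropping rule that is not written down, and the second guarantees only 30 days.

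Three stronger readings are tempting, and the documents do not support them.

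- A reader might infer that the cut-off makes late index years look like a driver of non-treatment. With untreated patients indexed at diagnosis and treated patients at prescription, the overall index-year gradient runs the other way, with a 2018 dip of about 1 point at medians of 3 to 6 months and essentially none at 12. The artefact appears by diagnosis year; for index year it also depends on which untreated index rule is chosen.
- A reader might infer serious bias in all comparisons with the untreated. At medians of 3 to 6 months, contamination is 1.4% to 4.1%.
- A reader might infer that most late-diagnosed untreated patients are future initiators. Under these assumptions it is about 9% to 19% of those diagnosed in the last 6 months.

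**Conclusion.** The point holds as a modest design gap. The reason given for waiving follow-up does not extend to assignment of the untreated cohort, and no binding rule elsewhere closes the gap. The likely effect is a small pull toward zero in the treated-versus-untreated standardized differences, enough to reclassify a characteristic near the 10% threshold but not one well above it.

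The existence of the gap rests on the text alone. Its size rests on an assumed lag of 3 to 12 months, uniform diagnoses, preliminary counts and future starters who resemble present ones. None of these is established in the documents, so the figures are a range and not an estimate. The nintedanib-versus-pirfenidone comparison and its propensity model are untouched. This is a cheap improvement worth making, not a threat to the study.

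**What to change.** In Section 9.2, limit the statement that no minimum follow-up is needed to the two drug cohorts. For the two treated-versus-untreated sets of standardized differences and the matching propensity model, require the earliest IPF diagnosis to fall at least X months before April 30, 2018. Apply this to treated and untreated patients alike. Pre-specify X (for example 6 or 12), and fix it before untreated characteristics are examined. Report X = 0 and other values of X as sensitivity analyses. A calendar cut-off has the advantage that it does not condition on survival after diagnosis.

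Do not set X from the raw 90th percentile of the treated cohorts' diagnosis-to-index interval; use that interval only as a guide. It is right-truncated at data end: observed lags have density proportional to (T − t)e^(−λt). For medians of 3, 6 and 12 months, the observed 90th percentile is about 9, 15 to 16 and 21 to 25 months, against true values (ln 10/λ) of 10, 20 and 40. It would also remove about 17% to 50% of diagnoses (percentile divided by T).

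The change needs a few sentences of protocol text and one date filter. The price at X = 12 is the sample loss in Step 5 and, at most, the rise in standard error in Step 6. If the lag is long, contamination is reduced but not eliminated, and Section 9.9 should say so.

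### The exploratory chest-CT criterion is ambiguous and on no reading gives a fixed look-back from diagnosis, so it can select on time from diagnosis to index

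*Combined protocol and SAP*

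**What the plan says.** The inclusion lists in Section 9.2 carry the same exploratory line for the nintedanib, pirfenidone and untreated cohorts, under which the plan may also require at least one "chest CT scan before first IPF diagnosis during the pre-index period". The same section defines the period: "The pre-index period for each cohort will be the 12 months prior to the index date".

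For treated patients, "The date of the first prescription will be defined as the index date". They also need an IPF code in the year before index ("With ≥ 1 diagnosis of IPF during the 12 months prior to the index date"), but it need not be their first ever.

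For untreated patients the index rule is left open. The inclusion list says "Index date will be defined as the date of the earliest IPF diagnosis or a randomly assigned date based on the exploratory analyses", and those analyses are to examine time from diagnosis to treatment in the treated cohorts. The index-date paragraph gives only a calendar range for the random option: "a randomly assigned date between October 1, 2013 and April 30, 2018". That range opens on the first day of data, since the study will "leverage the GE EMR data from October 1, 2013 to April 30, 2018".

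The line gives the CT no look-back of its own. Sections 9.9 (limitations) and 9.12 (bias) do not discuss the point.

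**The concern.** A CT criterion used to firm up a coded diagnosis should search the same stretch of time relative to diagnosis in every patient. This one mixes two anchors: the CT must precede a diagnosis, while the period named is counted back from index. The time between diagnosis and index then helps decide who can qualify.

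That matters because the study's result is the comparison of baseline characteristics. Sections 9.1 and 9.7.1 call an absolute standardized difference of 10% or more meaningful. Time from earliest diagnosis to index is itself reported for the treated cohorts (Section 9.3.3), and high-resolution CT is one of the compared procedures. A filter that depends on disease duration could truncate the first and alter the second. Where cohorts differ in delay, it could create differences by selection. The abstract also plans descriptions at different time points, which a look-back that grows with calendar time could disturb.

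**Working it through.** The plan states no CT count, pass rate or delay distribution, so there is no figure to reproduce. The check is window arithmetic on the dates in Section 9.2.

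**Notation.** D = months from earliest IPF code to index; W = length of the CT window in months.

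**Reading 1: CT inside the pre-index period and before the earliest IPF code.** The window runs from 12 months before index to D months before index, so W = max(0, 12 − D). To show what this could do, assume each patient's diagnostic CT falls uniformly in the L months before the code. The share captured is then min(1, W/L).

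| D | W | Captured, L = 6 | Captured, L = 3 |
|---|---|---|---|
| 0 | 12 | 100% | 100% |
| 6 | 6 | 100% | 100% |
| 9 | 3 | 3/6 = 50% | 100% |
| 10 | 2 | 2/6 = 33% | 2/3 = 67% |
| 11 | 1 | 1/6 = 17% | 1/3 = 33% |
| 12 or more | 0 | 0% | 0% |

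A second set of assumptions: 90% of patients have a recorded CT before diagnosis, and the gap from CT to diagnosis is exponential with mean m. The pass rate is 0.9 × (1 − exp(−W/m)).

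| | m = 1 month | m = 3 | m = 6 |
|---|---|---|---|
| D = 0 | 90% | 88% | 78% |
| D = 6 | 90% | 78% | 57% |
| D = 9 | 86% | 57% | 35% |
| D = 12 or more | 0% | 0% | 0% |
| D exponential, mean 3 | 88% | 82% | 67% |
| D exponential, mean 6 | 75% | 67% | 54% |
| D exponential, mean 12 | 54% | 46% | 36% |

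The D = 0 row is the comparator for untreated patients indexed at earliest diagnosis with a full year of data behind them. That year is not guaranteed: their look-back is min(12, months since 1 October 2013). A first code 3 months into the data leaves 3 months, and 3/6 = 50% capture under L = 6.

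**Reading 2: CT inside the period, with the first diagnosis meaning the first code in the period.** The window runs from the start of the period to that code. A patient first coded 20 months before index, whose first in-period code is 4 months before index, has 12 − 4 = 8 months. This patient can qualify, but the anchor is a repeat code, so the CT need not be the one that led to diagnosis.

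**Reading 3: the period limits the diagnosis and the CT is unbounded.** The look-back starts with the data on 1 October 2013 and ends at the anchoring code. It is at most 12 months for an index at the start of October 2014 and about 55 months for one at the end of April 2018, in each case less the time from that code to index. It therefore lengthens with calendar time. For an untreated patient indexed at earliest diagnosis there is no earlier code to anchor to, unless the index date counts as part of the period.

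**The case against.** The strongest reply is that the criterion is only something the plan will explore. It enters neither the Table 1 counts nor the analysis section. That stands, and it limits the weight of the point.

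A reader might infer that the line admits only CTs inside the 12 months and so necessarily selects the cohorts differently. The documents do not support that:

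- The ILD exclusion in the same lists uses the same period phrase, and there it attaches naturally to the diagnosis. Reading 1 is therefore one of several.
- The random untreated index date may be informed by the treated cohorts' delay. If it mirrors that delay, the window distributions match and the treated–untreated gap largely disappears.
- Nintedanib versus pirfenidone is affected only if their delays differ, and no figures are given.

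Nor can one say that slow-to-treat patients are always removed. On Reading 2 they can pass on a later CT. Nor do untreated patients always have a full 12 months, because of the data start. If CTs cluster close to diagnosis, the loss on Reading 1 is small until D is about 9 months.

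What survives is that no reading yields a fixed look-back from diagnosis, and the option that makes D = 0 for every untreated patient is still open.

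**Conclusion.** The point holds in conditional form. The wording is ambiguous, and each reading gives a CT window that varies with diagnosis-to-index time, with the placement of repeat codes, or with calendar time. The firm arithmetic result belongs to Reading 1: W = max(0, 12 − D), so a patient first coded 12 or more months before index cannot qualify.

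The criterion can therefore select on disease duration, and can do so differently for treated patients and for untreated patients indexed at diagnosis. How much is unknown. In the illustrations, the treated pass rate falls below the D = 0 rate by 2 points (90% − 88%: mean delay 3 months, CT gap 1 month) to 42 points (88% − 46%: mean delay 12 months, CT gap 3 months). All of these rest on assumed CT timing and delay. Because the criterion is exploratory, this is a cheap improvement to the plan and not a fault in its main analysis.

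**What to change.** If the criterion is explored, replace the line in all three cohorts with one rule: at least one chest CT in a fixed interval ending on the date of the earliest IPF code in the extract, for example the 6 months up to and including that date. Drop the pre-index limit. Ending the interval on the code date matters: a tail after the code, cut off at index, would give untreated patients indexed at diagnosis no extra days while treated patients could have some.

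Apply the rule among patients with that much recorded history before the code, report the number lost per cohort, and present the result as a sensitivity analysis. Settle the wording before cohort counts are seen.

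W is then 6 months whatever D is. Under the second set of assumptions the pass rate is 90%, 78% or 57% (m = 1, 3 or 6) in every cohort. A 12-month interval would give 90%, 88% or 78%, but needs twice the prior history.

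The cost is one line reworded in three places, plus a history requirement confined to the sensitivity analysis. With 6 months, patients first coded before about 1 April 2014 drop out of that analysis, including some with the longest delays. CTs before October 2013 or outside the network are still missed.
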